## 8.22 Management of Specific AEs

Management of certain AEs of concern are presented in the table below as they have been observed with this agent and are potentially immune related.

8.221 Pleural and pericardial effusion: Patients experiencing dyspnea, chest pain, or unexplained tachycardia should be evaluated for the presence of

a pericardial effusion. Patients with pre-existing pericardial effusion should be followed closely for pericardial fluid volume measurements and impact on cardiac function. When intervention is required for pericardial or pleural effusions, atezolizumab should be held, and appropriate workup includes cytology, lactate dehydrogenase (LDH), glucose, cholesterol, protein concentrations (with pleural effusions), and cell count.

- 8.222 Pulmonary events: Dyspnea, cough, fatigue, hypoxia, pneumonitis, and pulmonary infiltrates have been associated with the administration of atezolizumab. Patients will be assessed for pulmonary signs and symptoms throughout the study and will also have CT scans of the chest performed at every tumor assessment.

All pulmonary events should be thoroughly evaluated for other commonly reported etiologies such as pneumonia or other infection, lymphangitic carcinomatosis, pulmonary embolism, heart failure, chronic obstructive pulmonary disease, or pulmonary hypertension. Management guidelines for pulmonary events are provided in the table below.

- 8.223 Endocrine disorders: Patients experiencing one or more unexplained AEs possibly indicative of endocrine dysfunction (including fatigue, myalgias, impotence, mental status changes, and constipation) should be investigated for the presence of thyroid, pituitary, or adrenal endocrinopathies. The patient should be referred to an endocrinologist if an endocrinopathy is suspected. Thyroid-stimulating hormone (TSH) and free T3 and T4 levels should be obtained to determine whether thyroid abnormalities are present. TSH, prolactin, and a morning cortisol level will help to differentiate primary adrenal insufficiency from primary pituitary insufficiency. The table below describes dose management guidelines for hyperthyroidism, hypothyroidism, symptomatic adrenal insufficiency, and hyperglycemia.

- 8.224 Meningoencephalitis: Immune-related meningoencephalitis is an identified risk associated with the administration of atezolizumab. Immune-related meningoencephalitis should be suspected in any patient presenting with signs or symptoms suggestive of meningitis or encephalitis, including, but not limited to, headache, neck pain, confusion, seizure, motor or sensory dysfunction, and altered or depressed level of consciousness. Encephalopathy from metabolic or electrolyte imbalances needs to be distinguished from potential meningoencephalitis resulting from infection (bacterial, viral, or fungal) or progression of malignancy, or secondary to a paraneoplastic process.

All patients being considered for meningoencephalitis should be urgently evaluated with a CT scan and/or MRI scan of the brain to evaluate for metastasis, inflammation, or edema. If deemed safe by the treating physician, a lumbar puncture should be performed and a neurologist should be consulted.

Patients with signs and symptoms of meningoencephalitis, in the absence of an identified alternate etiology, should be treated according to the guidelines.

- 8.225 Neurologic disorders: Myasthenia gravis and Guillain-Barré syndrome have been observed with single-agent atezolizumab. Patients may present with signs and symptoms of sensory and/or motor neuropathy. Diagnostic work-up is essential for an accurate characterization to differentiate between alternative etiologies.
- 8.226 The table below presents management and dose modification guidelines for specific AEs. For recommendations to hold atezolizumab and begin corticosteroid treatment, use the following guidance for tapering the corticosteroid and resuming atezolizumab therapy after resolution of the event:
  - Corticosteroids must be tapered over  $\geq 1$  month to  $< 10$  mg/day oral prednisone or equivalent before atezolizumab can be resumed.
  - Atezolizumab may be held for a period of time beyond 12 weeks to allow for corticosteroids to be reduced to  $\geq 10$  mg/day oral prednisone or equivalent.
  - If the recommended course of action in the table below is to “permanently discontinue atezolizumab,” resumption of atezolizumab may be considered in patients who are deriving benefit and have fully recovered from the immune-related event under limited and compelling circumstances after consultation with the trial Principal Investigator.

| CTCAE SOC                  | Adverse Event         | Grade                  | Dose Adjustment and Management Recommendations  |
|----------------------------|-----------------------|------------------------|---|
| Endocrine disorders | Adrenal insufficiency | Grade 2+ (symptomatic) | Hold atezolizumab.
Refer patient to endocrinologist. Perform appropriate imaging.
Initiate treatment with 1-2 mg/kg/day intravenous methylprednisolone or equivalent and convert to 1-2 mg/kg/day oral prednisone or equivalent upon improvement.
Resume atezolizumab if event resolves to grade 1 or better and patient is stable on replacement therapy (if required) within 12 weeks.
Permanently discontinue atezolizumab and contact Medical Monitor if event does not resolve to grade 1 or better or patient is not stable on replacement therapy within 12 weeks. |
|                            | Hyperthyroidism       | Grade 1 (asymptomatic) | TSH $\geq 0.1$ mU/L and $< 0.5$ mU/L:
Continue atezolizumab. Monitor TSH every 4 weeks.
TSH $< 0.1$ mU/L:
Follow guidelines for symptomatic  |

| CTCAE SOC     | Adverse Event          | Grade                   | Dose Adjustment and Management Recommendations  |
|---------------|------------------------|-------------------------|---|
|               |                        |                         | hyperthyroidism.  |
|               |                        | Grade 2+ (symptomatic)  | Hold atezolizumab.
Initiate treatment with anti-thyroid drug such as methimazole or carbimazole as needed.
Consider patient referral to endocrinologist.
Resume atezolizumab when symptoms are controlled and thyroid function is improving.
Permanently discontinue atezolizumab and contact CTEP Medical Monitor for life-threatening immune-related hyperthyroidism.                   |
|               |                        | Grade 1 (asymptomatic)  | Continue atezolizumab.
Start thyroid-replacement hormone.
Monitor TSH weekly.   |
|               |                        | Grades 2+ (symptomatic) | Hold atezolizumab.
Start thyroid-replacement hormone.
Consider referral to an endocrinologist.
Monitor TSH weekly.
Restart atezolizumab when symptoms are controlled and thyroid function is improving.   |
| Eye disorders | Uveitis or retinopathy | Grade 1                 | Continue atezolizumab.
Patient referral to ophthalmologist is strongly recommended. Initiate treatment with topical corticosteroid eye drops and topical immunosuppressive therapy.
If symptoms persist, treat as a grade 2 event.  |
|               |                        | Grade 2                 | Hold atezolizumab.
Patient referral to ophthalmologist is strongly recommended. Initiate treatment with topical corticosteroid eye drops and topical immunosuppressive therapy.
Resume atezolizumab if event resolves to grade 1 or better within 12 weeks.
Permanently discontinue atezolizumab and contact Medical Monitor if event does not resolve to grade 1 or better within 12 weeks. |
|               |                        | Grade 3 or 4            | Permanently discontinue atezolizumab and contact Medical Monitor.
For grade 3, patient may only resume treatment after consultation with the trial PI; for grade 4, patient cannot resume treatment, regardless of benefit.
Refer patient to ophthalmologist.
Initiate treatment with 1-2 mg/kg/day oral prednisone or equivalent.   |

| CTCAE SOC                  | Adverse Event             | Grade     | Dose Adjustment and Management Recommendations  |
|----------------------------|---------------------------|-----------|---|
|                            |                           |           | If event resolves to grade 1 or better, taper corticosteroids over $\geq 1$ month   |
| Gastrointestinal disorders | Diarrhea or enterocolitis | Any grade | 
Patients should be advised to inform the investigator if any diarrhea occurs, even if it is mild.
 
All events of diarrhea or colitis should be thoroughly evaluated for other more common etiologies. For events of significant duration or magnitude or associated with signs of systemic inflammation or acute-phase reactants (e.g., increased CRP, f count, or bandemia): Perform sigmoidoscopy (or colonoscopy, if appropriate) with colonic biopsy, with three to five specimens for standard paraffin block to check for inflammation and lymphocytic infiltrates to confirm colitis diagnosis.
   |
|                            |                           | Grade 1   | 
Continue atezolizumab. Initiate symptomatic treatment.
 
Endoscopy is recommended if symptoms persist for <math>\geq 7</math> days. Monitor closely.
  |
|                            |                           | Grade 2   | 
Hold atezolizumab.
 
Initiate symptomatic treatment.
 
Patient referral to GI specialist is recommended.
 
For recurrent events or events that persist <math>> 5</math> days, initiate treatment with 1-2 mg/kg/day oral prednisone or equivalent.
 
Resume atezolizumab if event resolves to grade 1 or better within 12 weeks. If event resolves to grade 1 or better within 12 weeks, taper corticosteroids and resume atezolizumab according to the guidelines above.
 
Permanently discontinue atezolizumab and contact Medical Monitor if event does not resolve to grade 1 or better within 12 weeks. Resumption of atezolizumab may be considered in patients who are deriving benefit and have fully recovered from the immune-related event.
 |
|                            |                           | Grade 3   | 
Hold atezolizumab.
 
Refer patient to GI specialist for evaluation and confirmatory biopsy.
 
Initiate treatment with 1-2 mg/kg/day intravenous methylprednisolone or equivalent and convert to 1-2 mg/kg/day oral prednisone or equivalent upon
   |

| CTCAE SOC | Adverse Event                 | Grade        | Dose Adjustment and Management Recommendations  |
|-----------|-------------------------------|--------------|---|
|           |                               |              | 
improvement.
                     If event resolves to grade 1 or better within 12 weeks, taper corticosteroids and resume atezolizumab according to the guidelines above.
                     Permanently discontinue atezolizumab and contact Medical Monitor if event does not resolve to Grade 1 or better within 12 weeks. Resumption of atezolizumab may be considered in patients who are deriving benefit and have fully recovered from the immune-related event.
   |
|           |                               | Grade 4      | 
Permanently discontinue atezolizumab. Patient may not resume treatment, regardless of benefit.
                     Refer patient to GI specialist for evaluation and confirmation biopsy. Initiate treatment with 1-2 mg/kg/day intravenous methylprednisolone or equivalent and convert to 1-2 mg/kg/day oral prednisone or equivalent upon improvement.
                     If event does not improve within 48 hours after initiating corticosteroids, consider adding an immunosuppressive agent.
                     If event resolves to grade 1 or better, taper corticosteroids over <math>\geq 1</math> month. Resumption of atezolizumab may be considered in patients who are deriving benefit and have fully recovered from the immune-related event.
 |
|           | Pancreatitis (immune related) | Grade 2 or 3 | 
Hold atezolizumab.
                     Refer patient to GI specialist.
                     Initiate treatment with 1-2 mg/kg/day intravenous methylprednisolone or equivalent and convert to 1-2 mg/kg/day oral prednisone or equivalent upon improvement.
                     Resume atezolizumab if event resolves to grade 1 or better within 12 weeks.
                     Permanently discontinue atezolizumab and contact Medical Monitor if event does not resolve to grade 1 or better within 12 weeks.
                     For recurrent events, permanently discontinue atezolizumab and contact Medical Monitor. Patient may not resume treatment, regardless of benefit.
  |
|           |                               | Grade 4      | 
Permanently discontinue atezolizumab and contact Medical Monitor. Patient may not resume treatment, regardless of
  |

| CTCAE SOC                          | Adverse Event                             | Grade                       | Dose Adjustment and Management Recommendations  |
|------------------------------------|---|-----------------------------|---|
|                                    |   |                             | 
benefit
 
Refer patient to GI specialist.
 
Initiate treatment with 1-2 mg/kg/day intravenous methylprednisolone or equivalent and convert to 1-2 mg/kg/day oral prednisone or equivalent upon improvement.
 
If event does not improve within 48 hours after initiating corticosteroids, consider adding an immunosuppressive agent.
 
If event resolves to grade 1 or better, taper corticosteroids over 1 month.
  |
| Infections and infestations | Meningitis or encephalitis                | All grades                  | 
Permanently discontinue atezolizumab and contact Medical Monitor. Patient may not resume treatment, regardless of benefit.
 
Refer patient to neurologist.
 
Initiate treatment with 1-2 mg/kg/day IV methylprednisolone or equivalent and convert to 1-2 mg/kg/day oral prednisone or equivalent upon improvement.
 
If event resolves to grade 1 or better, taper corticosteroids over <math>\geq 1</math> month. If event does not improve within 48 hours after initiating corticosteroids, consider adding an immunosuppressive agent.
 |
| Investigations              | Lipase increase or serum amylase increase | Grade 1
>ULN - 1.5 x ULN | 
Continue atezolizumab.
 
Monitor amylase and lipase prior to dosing.
  |
|                                    |   | Grade 2 (>1.5 - 2.0 x ULN)  | 
Continue atezolizumab.
 
Monitor amylase and lipase weekly.
   |

| CTCAE SOC                                 | Adverse Event  | Grade  | Dose Adjustment and Management Recommendations   |
|---|--|--|--|
|   |  | Grade 3 (>2.0 - 5.0 x ULN) or 4 (>5.0 x ULN) | 
Hold atezolizumab.
 
Refer patient to gastrointestinal (GI) specialist. Monitor amylase and lipase every other day.
 
If no improvement, consider treatment with 1-2 mg/kg/day oral prednisone or equivalent.
 
Resume atezolizumab if event resolves to grade 1 or better within 12 weeks.
 
Permanently discontinue atezolizumab and contact Medical Monitor if event does not resolve to grade 1 or better within 12 weeks.
 
For recurrent events associated with pancreatitis symptoms, permanently discontinue atezolizumab and contact Medical Monitor. Treatment for recurrent events not associated with pancreatitis symptoms may be resumed after consultation with the trial Principal Investigator.
 |
| Metabolism and nutrition disorders | Hyperglycemia  | Grade 1 or 2                                 | 
Continue atezolizumab.
 
Initiate treatment with insulin if needed.
 
Monitor for glucose control.
  |
|   |  | Grade 3 or 4                                 | 
Hold atezolizumab.
 
Initiate treatment with insulin. Monitor for glucose control.
 
Resume atezolizumab when symptoms resolve and glucose levels are stable.
   |
| Nervous system disorders           | Peripheral motor neuropathy or Peripheral sensory neuropathy | Grade 1                                      | 
Continue atezolizumab.
 
Evaluate for alternative etiologies.
  |
|   |  | Grade 2                                      | 
Hold atezolizumab.
 
Evaluate for alternative etiologies.
 
Initiate treatment as per institutional guidelines.
 
Resume atezolizumab if event resolves to grade 1 or better within 12 weeks.
 
Permanently discontinue atezolizumab and contact Medical Monitor if event does not resolve to grade 1 or better within 12 weeks.
  |
|   |  | Grade 3 or 4                                 | 
Permanently discontinue atezolizumab and contact Medical Monitor. Initiate treatment as per institutional guidelines.
   |
| Respiratory, thoracic and          | All pulmonary events   | All grades                                   | Evaluate thoroughly for other commonly reported etiologies such as   |

| CTCAE SOC  | Adverse Event                         | Grade               | Dose Adjustment and Management Recommendations  |
|--|---------------------------------------|---------------------|---|
| 
mediastinal disorders
                  |                                       |                     | 
pneumonia/infection, lymphangitic carcinomatosis, pulmonary embolism, heart failure, chronic obstructive pulmonary disease (COPD), or pulmonary hypertension.
  |
|  |                                       | 
Grade 1
      | 
Continue atezolizumab and monitor closely. Re-evaluate on serial imaging. Consider patient referral to a pulmonary specialist.
For recurrent pneumonitis, treat as a grade 3 or 4 event.
   |
|  |                                       | 
Grade 2
      | 
Hold atezolizumab.
Refer patient to pulmonary and infectious disease specialists and consider bronchoscopy or bronchoscopic alveolar lavage (BAL).
Initiate treatment with 1-2 mg/kg/day oral prednisone or equivalent. Resume atezolizumab if event resolves to grade 1 or better within 12 weeks (consult tapering guideline above).
Permanently discontinue atezolizumab and contact Medical Monitor if event does not resolve to grade 1 or better within 12 weeks.
For recurrent events, treat as a Grade 3 or 4 event.
                               |
|  |                                       | 
Grade 3 or 4
 | 
Permanently discontinue atezolizumab and contact Medical Monitor. For grade 3, patient may only resume treatment after consultation with the trial PI For grade 4, patient may not resume treatment, regardless of benefit.
Bronchoscopy or BAL is recommended.
Initiate treatment with 1-2 mg/kg/day oral prednisone or equivalent.
If event does not improve within 48 hours after initiating corticosteroids, consider adding an immunosuppressive agent.
If event resolves to grade 1 or better, taper corticosteroids over <math>\geq 1</math> month.
 |
| 
Skin and subcutaneous tissue disorders
 | 
Rash maculo-papular or purpura
 | 
Grade 1
      | 
Continue atezolizumab.
Consider topical steroids and/or other symptomatic therapy (e.g., antihistamines).
  |
|  |                                       | 
Grade 2
      | 
Continue atezolizumab. Consider dermatologist referral. Administer topical corticosteroids.
Consider higher potency topical corticosteroids if event does not improve.
   |

| CTCAE SOC  | Adverse Event | Grade  | Dose Adjustment and Management Recommendations   |
|--|---------------|--|--|
|  |               | Grade 3  | Hold atezolizumab.
Refer patient to dermatologist. Administer oral prednisone 10 mg or equivalent. If the event does not improve within 48-72 hours, increase dose to 1–2 mg/kg/day or equivalent.
Restart atezolizumab if event resolves to grade 1 or better within 12 weeks.
Permanently discontinue atezolizumab and consult CTEP Medical Monitor if event does not resolve to grade 1 or better within 12 weeks. |
|  |               | Grade 4  | Permanently discontinue atezolizumab and contact CTEP Medical Monitor. Patient may not resume treatment, regardless of benefit.  |
|  |               | Persistent and/or severe rash or pruritus, any grade | A dermatologist should evaluate the event. A biopsy should be performed unless contraindicated.  |
| 
Symptoms of abdominal pain associated with elevations of amylase and lipase, suggestive of pancreatitis, have been associated with administration of other immunomodulatory agents. The differential diagnosis of acute abdominal pain should include pancreatitis. Appropriate workup should include an evaluation for obstruction, as well as serum amylase and lipase tests. See the guidelines for “Amylase and/or lipase increase” and “Immune-related pancreatitis” elsewhere in this table, as needed.
 
Right upper-quadrant abdominal pain and/or unexplained nausea or vomiting should be evaluated for potential hepatotoxicity (see the “Hepatotoxicity” guideline elsewhere in this table).
 |               |  |  |
| 
Myasthenia gravis and Guillain-Barré syndrome All grades Permanently discontinue atezolizumab and contact Medical Monitor. Patient may not resume treatment, regardless of benefit. Refer patient to neurologist. Initiate treatment as per institutional guidelines. Consider initiation of 1-2 mg/kg/day oral or IV prednisone or equivalent.
   |               |  |  |

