## **8.2 Treatment Delay and Dose Reduction of Atezolizumab**

### **8.21 General AE Management and Dose Modification Guidelines**

There will be no dose reduction for atezolizumab in this study. Patients may temporarily suspend study treatment for up to 84 days (12 weeks) beyond the scheduled date of delayed infusion if study drug-related toxicity requiring dose suspension is experienced. If atezolizumab is held because of AEs for  $\geq 84$  days beyond the scheduled date of infusion, the patient will be discontinued from atezolizumab and will be followed for safety and efficacy as specified in this protocol.

If a patient must be tapered off steroids used to treat AEs, atezolizumab may be held for additional time beyond 84 days (12 weeks) from the scheduled dose until steroids are discontinued or reduced to a prednisone dose (or dose equivalent) of 10 mg/day. The acceptable length of interruption will be at the discretion of the investigator.

Dose interruptions for reasons other than toxicity, such as surgical procedures, may be allowed.

Any toxicity associated or possibly associated with atezolizumab treatment should be managed according to standard medical practice. Additional tests, such as autoimmune serology or biopsies, may be used to determine a possible immunogenic etiology. Although most immune-related adverse events (irAEs) observed with immunomodulatory agents have been mild and self-limiting, such events should be recognized early and treated promptly to avoid potential major complications (20) (Appendix C). Discontinuation of atezolizumab may not have an immediate therapeutic effect, and there is no available antidote for atezolizumab. In severe cases, immune-related toxicities may be acutely managed with topical corticosteroids, systemic corticosteroids, or other immunosuppressive agents. The investigator should consider the benefit-risk balance prior to further administration of atezolizumab. In patients who have met

the criteria for permanent discontinuation, resumption of atezolizumab may be considered if the patient is deriving clinical benefit and has fully recovered from the immune-related event.

Patients can be re-challenged with atezolizumab ONLY after careful consideration of benefit- risk balance and medical judgment by the trial Principal Investigator. Atezolizumab may NOT be resumed if the patient experiences any of the following events, regardless of benefit:

- Grade 3 or 4 pneumonitis

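### Sections 8.226 and 8.21 give inconsistent steroid thresholds for ending an extended atezolizumab hold and for resuming the drug

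*Combined protocol and SAP*

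**What the plan says.** Three statements in the protocol bear on the steroid dose at which a hold of atezolizumab ends or the drug is restarted.

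- **Section 8.226, first bullet** (under 8.22, Management of Specific AEs). The steroid must be tapered, over a month or longer, to less than 10 mg/day "oral prednisone or equivalent before atezolizumab can be resumed".
- **Section 8.226, second bullet.** "Atezolizumab may be held for a period of time beyond 12 weeks to allow for corticosteroids to be reduced to" a dose printed with a greater-than-or-equal sign, that is, 10 mg/day or more.
- **Section 8.21, General AE Management and Dose Modification Guidelines.** A hold may run past 84 days (12 weeks) for a patient who is being tapered, "until steroids are discontinued or reduced to a prednisone dose (or dose equivalent) of 10 mg/day". The next sentence adds: "The acceptable length of interruption will be at the discretion of the investigator".

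Section 8.226 presents its bullets as a single set of instructions: "use the following guidance for tapering the corticosteroid and resuming atezolizumab therapy after resolution of the event". Section 8.21 also says that a patient held for adverse events for 84 days or more past the scheduled infusion is taken off atezolizumab; the steroid taper is the exception to that. Nothing in the protocol says which of the three statements takes precedence.

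**The concern.** The extended hold exists so that a patient on a long taper can reach a steroid dose at which atezolizumab may be restarted. The dose that ends the extension and the dose that permits restarting should therefore fit together. As printed, they do not: adjacent bullets carry opposite inequality signs around the same number, and Section 8.21 gives the number with no sign.

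The rule is in active use. The adverse event table that follows 8.226 refers back to it for Grade 2 and Grade 3 diarrhea or enterocolitis and for Grade 2 pulmonary events. At stake is whether sites apply the same rule to a patient recovering from an immune-related event, and whether a patient past day 84 is still within the steroid-taper exception or should be discontinued.

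**Working it through.** No sample size, power or error rate is involved, so there is no plan figure to reproduce. The check sets the three statements side by side as conditions on the daily prednisone-equivalent dose, d, in mg/day.

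**Inputs**

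- 8.226, first bullet: resumption requires d < 10.
- 8.226, second bullet: the target of a hold beyond 12 weeks is d ≥ 10.
- 8.21: a hold beyond 84 days runs until d = 10 or steroids are stopped. 84 days ÷ 7 = 12 weeks, so this and the second bullet describe the same extension.

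**Step 1: as printed**

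| Dose | 8.226 bullet 1: may resume? | 8.226 bullet 2: target met? | 8.21: end-point reached? |
|---|---|---|---|
| Below 10 | Yes, once the taper has lasted the required time | No | Yes if steroids are stopped; otherwise the dose is already past 10 |
| Exactly 10 | No | Yes | Yes |
| Above 10 | No | Yes | No |

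The sets d < 10 and d ≥ 10 do not overlap, so no dose meets both 8.226 bullets. The second bullet is also met by every dose above 10 mg/day. A patient at such a dose already satisfies it before any taper, so it cannot define the end of one.

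**Step 2: suppose the second bullet's sign should be ≤**

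The second bullet then agrees with 8.21 at exactly 10 mg/day, and the direct opposition between the bullets disappears. At d = 10, however, the second bullet and 8.21 are both satisfied while the first bullet still bars resumption.

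**Step 3: set the second bullet aside altogether**

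At d = 10 the 8.21 end-point is reached and the first bullet of 8.226 still bars resumption. The boundary conflict therefore does not depend on the doubtful sign.

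**Step 4: consequence past day 84**

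Take a patient held for more than 84 days whose dose has come down to exactly 10 mg/day. Under 8.21 the reason for extending the hold has ended. Under 8.226 the drug cannot yet be restarted. The protocol does not say whether the hold may continue while the dose falls further, or whether the general 84-day discontinuation now applies.

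**The case against.** **The statements do different jobs.** Only the first bullet of 8.226 sets a steroid dose for restarting. The second bullet and 8.21 are permissive and concern how long a hold may last. This is correct. A reader might infer that the second bullet allows atezolizumab to be restarted at 10 mg/day or more, but the text does not say so; a literal reader still finds one resumption condition, d < 10. What remains is that the end of the hold and the start of dosing do not meet.

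**Two of the three agree at the boundary.** A reader might infer that all three statements give different answers at 10 mg/day. They do not: there, 8.21 and the second bullet are both met, and only the first bullet is not.

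**The sign may not be real.** The text was machine-read, and a reversed sign could come from that or from a typing slip in the source. This cannot be settled from the text. Steps 2 and 3 show that the boundary conflict survives either way, but the opposite-sign finding should be held with that reservation.

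**Hold length is already discretionary.** Section 8.21 leaves the acceptable interruption to the investigator. This softens the effect on duration, since an investigator could rely on it to keep holding. It does not change the dose condition for restarting or say how the discretion sits with the 84-day discontinuation.

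**The reach is limited.** A reader might infer that the rule touches every patient given steroids, or that it decides who stops atezolizumab for good. The adverse event table does not support either. Permanent discontinuation there turns mostly on event type and grade, or on failure to improve to Grade 1 within 12 weeks. Some events bar any restart, and others are managed with topical steroids while the drug continues. Section 8.21 and the third bullet of 8.226 also allow restarting to be considered, with listed exceptions, after discontinuation criteria are met.

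**The primary endpoint is not shown to be affected.** A reader might infer that inconsistent resumption distorts the response analysis. Under 16.11, eligible, consented patients who have begun treatment stay evaluable unless they are a major violation, and 13.8 ties that term to cycle 1 treatment. The denominator does not move, and no effect on response can be derived.

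**Conclusion.** The inconsistency stands as a wording fault in an operative safety rule. On the printed text, the two 8.226 bullets cannot both be met at any dose, and the second cannot serve as a taper target. If its sign is wrong, the remaining conflict is confined to exactly 10 mg/day, where 8.21 ends the extended hold and 8.226 does not yet allow resumption; past 84 days the patient's status is then undefined.

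The patients concerned are those whose atezolizumab is held while corticosteroids are given for an immune-related event, mainly those whose taper lasts beyond 12 weeks. The documents give no rate from which to estimate how many that is. Sample size, the two-stage decision rule and error rates are unaffected.

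The conclusion assumes that the three statements are meant to work as one taper-and-resume rule. The shared introduction in 8.226 and the matching 12-week limit in 8.21 support that reading. No view is taken on which threshold is clinically right.

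**What to change.** Check the sign in the second 8.226 bullet against the source document. Then reconcile both 8.226 bullets and the 8.21 sentence so that the end-point of the extended hold and the condition for resuming use one consistent threshold and one inequality direction. The sponsor should choose the value. The same edit should state what happens to a patient past 84 days who has reached the end-point of the hold but does not yet meet the condition for resuming, if the chosen wording leaves any such case.

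The cost is a change to three sentences of protocol text. No statistical section, sample size or analysis needs to be revised.
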